F.1.4. Active and run-in patch dosing: Because data from our pilot study suggest that doses of 0.2 mg/hr or higher are more likely to result in meaningful improvement in hot flashes (see Preliminary Data section), we will use only 0.2, 0.4, and 0.6 mg/hr dosages of NTG during the active phase of the trial. For logistical reasons, the 0.6 mg/hr dosage will be obtained through simultaneous use of a 0.2 and 0.4 mg/hr patch, rather than a 0.6 mg/hr patch. Additionally, a 0.1 mg/hr patch will be used during a brief 3-day run-in period prior to randomization, to eliminate women who are unable to self-administer and tolerate even the lowest dose of transdermal NTG.

F.1.5. Schedule of administration during run-in: During the brief run-in period, women will apply a 0.1 mg/hr NTG patch to their chest or any clean, dry, hairless area of skin on the body except the extremities below the knee or elbow. Women will self-administer this patch at home daily (removing the old patch each night and replacing it with a new patch) for 3 days. Women will also be advised to rotate the location of the patch on a nightly basis to minimize risk of skin reaction or breakdown. Those who report persistent or significant

headache, develop skin reaction, hypotension, or severe hypertension at the baseline visit, or are otherwise unable to apply patches daily during run-in, will not continue to randomization.

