F.1.6. Schedule of administration during treatment phase: At the baseline visit, women who successfully complete the run-in with 0.1 mg/hr NTG and meet all eligibility criteria will be assigned in a 1:1 ratio to start using a 0.2 mg/hr NTG or identical-appearing placebo patch for the treatment phase of the study. Women will again apply a new patch each night, directly after removing the old one, and avoiding patch-free episodes that could interfere with maintenance of nitrate tolerance. At a 1-week follow-up visit, those who report persistent hot flashes, do not have blood pressure <90/60 or >180/110, and pose no other major safety or tolerability issue will have their NTG (or placebo) dose increased to 0.4 mg/hr. Based on the 2-week follow-up visit, women with persistent hot flashes and no significant blood pressure, safety, or tolerability issue will have their dose increased to 0.6 mg/hr and remain at this for the remainder of the study. Women who report being completely satisfied on a dose lower than 0.6 mg/hr or who have major safety or tolerability issues will be permitted to remain on a lower dose.

F.1.7. Discontinuation of NTG/placebo after treatment phase: At the 12-week visit, participants will be asked to wean off NTG (or placebo) over the next 1 to 3 days, by decreasing their patch dose on a nightly basis before stopping NTG/placebo completely. Specifically, participants who are being weaned from the 0.6 mg dose of study medication will be instructed to switch to 0.4 mg for one day, then to 0.2 mg for one day, then to stop study drug altogether. Participants who are being weaned from the 0.4 mg dose will switch to 0.2 mg for one day before stopping medication altogether. Women who are taking the 0.2 mg (the lowest dose hypothesized to have a therapeutic effect) will simply stop study medication without any change in dose. Women will be given a last supply of NTG or placebo medication (one patch of each dose strength needed to complete the weaning). Participant and staff blinding will be maintained throughout the weaning process; for participants taking placebo, weaning will use placebo rather than active NTG patches. In the event that a participant develops a potentially severe adverse event such as chest pain during weaning, she will be directed to seek immediate emergency attention, just as she would during any other time point of the study.

F.2 Concomitant Interventions

F.2.1 Allowed interventions

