Following run-in, eligible women will be randomized in equal ratios to the NTG or placebo interventions using a computer algorithm with randomly permuted blocks of size 2 and 4. To ensure similar distribution of women of different menopausal stages in each group, randomization will be stratified by menopausal stage (i.e., postmenopausal vs late menopausal transition), although there will be no pre-set sample size threshold for any specific stratum. Within each category, randomization numbers identifying the supply of medication for each participant will be generated and then assigned sequentially in the order participants are randomized.

To avoid manipulation of randomization, standard allocation concealment procedures will be followed (Schulz and Grimes 2002). Randomization numbers will be pre-printed on medication foil packets and master packs, prepared by Clinical Trials Services. At baseline, after screening data have been reviewed and the principal investigator has confirmed eligibility, a coordinator will enter the date and participant ID into the randomization log next to the number that has not yet been assigned, and dispense a supply of the drug identified by the randomization number. To provide a check on validity, an analyst will check that the randomization dates and times follow the order of the sequence numbers.

Based upon randomization, participants will be given a supply of either 0.2 mg/hr NTG or placebo patches and will be instructed to apply their first patch that night and change their patches on a nightly basis, without any patch-free periods, until the 1-week visit.

C. Blinding

Consistent with a double-blinded design, participants, investigators, and any study staff who have contact with participants or role in assessing outcomes will be blinded to treatment assignment. Only the statistician responsible for generating the randomization scheme and the staff of Clinical Trials Services contracted to package the active and placebo patches will have access to treatment assignment. Unless stipulated by the Data & Safety Monitoring Board or required for management of a participant with a serious adverse event, assignment codes will not be broken until all participants have completed the study, the trial data are cleaned, and the dataset is locked.

H.2.5 Follow-up visits

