Follow-up visits will consist of a 1-week clinic visit, 2-week clinic visit, 5-week clinic visit, 8-week telephone call, 12-week clinic visit, and 4-week post-discontinuation telephone call. These visits will be conducted by coordinators based at outpatient research facilities on the Mt. Zion campus of UCSF or in rented facilities in surrounding counties, or through secure video-based platforms.

A. 1-Week Clinic Visit

- Approximately 1 week after randomization, women will return for an in-person or video-based visit, bringing their study medication diaries and any unused medication.
- Potentially severe side effects of NTG will be systematically assessed and recorded, and other unanticipated adverse events that are reported will also be documented according to standard protocols.
- Study coordinators will review medication diaries and tabulate unused patches to assess adherence and trouble-shoot barriers to adherence.
- Two resting blood pressure and heart rate measurements and orthostatic measurements will be obtained by a trained study coordinator.
- Women who report no symptoms of hypotension or other safety issues, have blood pressures

within acceptable parameters, and continue to report bothersome hot flashes will be asked to increase to the 0.4 mg/hr NTG patch (or identical placebo) at this visit. Those who are not eligible or who decline to increase to 0.4 mg/hr will be permitted to remain on 0.2 mg/hr.

- Women who are not yet postmenopausal will be reminded to refrain from sexual activity or use barrier contraceptives; those who report unprotected sexual activity will be asked to provide a urine sample for pregnancy testing.
- An appropriate supply of study medication (or placebo) will be dispensed, and participants will be asked to apply NTG or placebo patches on a nightly basis leading up to the 2-Week Clinic Visit.

B. 2-Week Clinic Visit

- Approximately 2 weeks after randomization, women will return for an in-person or video-based visit, bringing their study medication logs and any unused medication.
- Potentially severe side effects of NTG will be systematically assessed and recorded, and other unanticipated adverse events that are reported will also be documented according to standard protocols.
- Study coordinators will review medication diaries and tabulate unused patches to assess adherence and trouble-shoot barriers to adherence.

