At all on-treatment interim follow-up visits (i.e., 1-week, 2-week, 5-week), transdermal NTG will be decreased or stopped in women with blood pressures <90/60 mm Hg (both measurements), or in those with blood pressures <100/60 mm Hg and symptoms such as dizziness that are suggestive of hypotension. Study medication will also be decreased or stopped in women with symptoms such as dizziness who have a resting blood pressure in the normal range but demonstrate orthostatic changes in blood pressure or heart rate when rising from the supine to standing position. These

women will also be given a standardized letter documenting their blood pressure reading to take to their regular health care provider to promote further monitoring and/or evaluation. In the event that there is a concern about the reliability of clinic measurements, or women report symptoms suggestive of hypotension despite having blood pressure measurements in the normal range, home-based or ambulatory blood pressure measurements will be obtained, to detect episodes of hypotension that may have been missed by clinic measurements. In the (hopefully unlikely) event that a participant reports a recent episode of syncope or loss of consciousness, study staff will also urge the participant to seek emergency medical attention.

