Hypertension: Potential participants will undergo measurement of blood pressure at both the screening and baseline visits, and those with blood pressure $>180/110$ at baseline will be excluded from the study due to the theoretical risk of increased blood pressure with induction of nitrate cross-tolerance. (Women may still seek further anti-hypertension therapy from their regular sources of health care and re-present for screening if desired). At all on-treatment interim follow-up visits (i.e., 1-week, 2-week, 5-week), blood pressure will be reassessed, and transdermal NTG will be decreased or stopped in women with blood pressures $>180/110$ mm Hg. Women with blood pressure $>180/110$ at any study visit will also be urged to seek emergency medical attention. Additionally, women with blood pressures $>160/100$ will be given a standardized letter to take to their regular health care provider to promote further evaluation and/or treatment. In the event that there is a concern about the reliability of clinic measurements, or women report high blood pressure measurements obtained elsewhere despite having blood pressure measurements in the normal range at their study visits, home-based or ambulatory blood pressure measurements may be obtained, to detect uncontrolled hypertension that may have been missed by in the study clinic. At the end of the treatment period, participants will be weaned off study medication rather than discontinuing medication abruptly, to minimize any risk of rebound hypertension.

Skin irritation: Women with known allergy to adhesives will be excluded, as these women may have a more significant reaction to the adhesive associated with the transdermal NTG patch. Women will also be advised to rotate the location of the patch on a nightly basis to minimize risk of skin reaction or breakdown. During the brief run-in period with the 0.1 mg/hr NTG patch, women who are unable to tolerate the patch will be excluded. If women subsequently develop significant skin irritation in response to using the transdermal nitrate (or placebo) patch, their participation in the study will be terminated early.

B. Protections against potential risks associated with other study data collection procedures:

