Study medication may be discontinued if deemed necessary to protect the safety of a participant or preserve the integrity of the study. The decision to discontinue study medication will be made on a case-by-case by the principal investigator, with input from the steering committee and the DSMB as needed. In most cases, discontinuation of study medication will prompt early termination of study participation, although there may be select cases where study medications are discontinued only temporarily, and the participant is subsequently restarted on study medication and then followed for the full duration of the study.

Specific reasons for discontinuation of study medication and/or early termination of the study include: 1) syncopal episode attributable to NTG-induced hypotension or vasodilation; 2) development of persistent blood pressure <90/60, blood pressure <100/60 with symptoms of dizziness, or orthostatic blood pressure with symptoms of dizziness, which do not resolve with reduction in study medication dose; 3) development of persistent severe hypertension defined by blood pressure >180/110; 4) development of pregnancy or decision to try to become pregnant (among women who are not yet postmenopausal); 5) development of another clinically significant adverse event limiting a participant's ability to safely continue to use the study drug; 6) unusually disruptive behavior exhibited by a participant during study visits that endangers the safety or well-being of the participant or study staff; or 7) decision to terminate the study by the IRB, the NIA, or other regulatory bodies.

Participants may also withdraw voluntarily from participation in the study at any time and for any reason. If a participant decides to discontinue the study drug or withdraw from the study, the study coordinator will try to elicit the reason for this decision. The coordinator may also try to trouble-shoot participant concerns or discuss strategies for overcoming barriers to continued participation in the study in order to try to retain the participant, provided that the decision to terminate is not driven by a safety issue.

J.2 Discontinuation/Termination Procedures

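### At week 1, on 0.2 mg/hr, the visit instructions let a woman with out-of-range blood pressure stay on her dose, the safety section says reduce or stop, and the treatment phase has no lower dose

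*Combined protocol and SAP*

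**What the plan says.** All references are to the combined protocol and SAP.

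- **H.1.4 B (Randomization):** "participants will be given a supply of either 0.2 mg/hr NTG or placebo patches", to be used until the 1-week visit.
- **H.2.5 A (1-Week Clinic Visit):** women without hypotension symptoms or other safety issues, whose blood pressures are "within acceptable parameters, and continue to report bothersome hot flashes will be asked to increase to the 0.4 mg/hr NTG patch" or its placebo. For the rest: "Those who are not eligible or who decline to increase to 0.4 mg/hr will be permitted to remain on 0.2 mg/hr". H.2.5 B has a parallel sentence at week 2.
- **F.1.6:** blood pressure below 90/60 or above 180/110 blocks the week-1 increase. Women "who have major safety or tolerability issues will be permitted to remain on a lower dose".
- **I.1.2, Lightheadedness/hypotension:** for the 1-, 2- and 5-week visits, "transdermal NTG will be decreased or stopped in women with blood pressures <90/60 mm Hg (both measurements". The same applies below 100/60 with symptoms such as dizziness, and to symptomatic orthostatic change with normal resting pressure.
- **I.1.2, Hypertension:** at the same visits, "transdermal NTG will be decreased or stopped in women with blood pressures" above 180/110.
- **F.1.4:** "we will use only 0.2, 0.4, and 0.6 mg/hr dosages of NTG during the active phase of the trial". The 0.1 mg/hr patch is for the run-in.
- **J.1, criterion 2:** the low-pressure and orthostatic findings are reasons for discontinuation when they are ones "which do not resolve with reduction in study medication dose".

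**The concern.** A coordinator who works from the visit procedures and one who works from the safety section could act differently on the same reading, at the same visit, in the same woman. H.2.5 A and F.1.6 contain no exception for women who meet an I.1.2 limit and do not refer to that section. No order of precedence is stated anywhere.

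Patient safety is the main issue: a limit written to protect participants should give one instruction at the first visit on randomized treatment. There is a lesser consequence for the data. J.1 says that stopping study drug will in most cases end participation, so the section followed can decide who is still in the study for the 5-week and 12-week diaries.

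**Working it through.** No sample size, power or error rate is involved. The check sets the sections side by side for a woman at the 1-week visit, whose dose must be 0.2 mg/hr (H.1.4 B).

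| Finding at week 1 | H.2.5 A and F.1.6 | I.1.2 | J.1 |
|---|---|---|---|
| Both readings below 90/60 | No increase; may stay on 0.2 | Reduce or stop | Listed reason if persistent and unresolved after a reduction |
| Below 100/60 with dizziness | No increase (symptoms); may stay on 0.2 | Reduce or stop | Listed reason if unresolved after a reduction |
| Symptomatic orthostatic change, normal resting pressure | No increase (symptoms); may stay on 0.2 | Reduce or stop | Listed reason if unresolved after a reduction |
| Above 180/110 | No increase; may stay on 0.2 | Reduce or stop | Listed reason if persistent; no reduction condition |
| Pressure in range, no symptoms, hot flashes not bothersome | No increase; may stay on 0.2 | No rule triggered | No rule triggered |

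1. The first four rows conflict: staying on 0.2 mg/hr is neither a reduction nor a stop. The last row shows where there is no conflict, so the problem is confined to women who meet an I.1.2 limit.
2. F.1.4 gives treatment-phase doses of 0.2, 0.4 and 0.6 mg/hr, so there are none below 0.2. The weaning text in F.1.7 and J.2 agrees: from 0.2 mg/hr the woman simply stops. Of the two actions in I.1.2, reduction cannot be carried out at this dose.
3. For the same reason the condition in J.1 criterion 2 cannot be tested in a woman on 0.2 mg/hr. This concerns low pressure and orthostatic findings only; criterion 3, on severe hypertension, carries no such condition.
4. The low limit is worded differently across sections. I.1.2 requires both measurements below 90/60, F.1.6 does not say how many, and J.1 speaks of persistence.
5. At week 2 the H.2.5 B sentence recreates the conflict for women still on 0.2 mg/hr. At week 5 the visit text has no such sentence, but for women still on 0.2 mg/hr the reduction option and the J.1 condition remain unusable.

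Time to the next scheduled reading for a woman kept on 0.2 mg/hr at week 1, from the H.2.8 windows (week 1 = days 4 to 10, week 2 = days 11 to 17): shortest 11 − 10 = 1 day, longest 17 − 4 = 13 days.

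**The case against.** The strongest reply is that the sections can largely be read together. H.2.5 A is permissive and is about who escalates; I.1.2 is mandatory and specific to blood pressure, so a sensible reader would let it govern. I.1.2 also offers two actions and can still be followed at 0.2 mg/hr by stopping. J.1 is discretionary and case by case, and its criterion 5 (another clinically significant adverse event) could cover a woman on 0.2 mg/hr. Affected women should be few: screening and run-in remove those with out-of-range readings, and in the pilot nobody stopped for hypotension and nobody developed new hypertension.

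Most of this stands, and it narrows the point. It does not supply the missing exception or a precedence rule, and stopping still contradicts permission to stay.

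Several stronger readings are tempting, but the documents do not support them:

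- **That no lower patch exists.** A 0.1 mg/hr patch is purchased (F.1.1), but F.1.4 keeps it for the run-in. The correct statement is that there is no lower treatment-phase dose.
- **That I.1.2 amounts to an instruction to stop at 0.2 mg/hr.** Stopping is the only one of its two actions that the listed doses allow, but the plan does not say that this was intended.
- **That J.1 gives a third, competing instruction.** At 0.2 mg/hr its reduction condition simply cannot be applied; the conflict is between H.2.5 A with F.1.6 and I.1.2.
- **That the pilot shows how many are affected.** C.3 reports three women who stayed on 0.2 mg/hr, but by preference, not for blood pressure.
- **That the woman goes unmeasured for weeks.** The gaps between later visits are long: 29 − 17 = 12 to 41 − 11 = 30 days from week 2 to week 5, and 78 − 41 = 37 to 90 − 29 = 61 days from week 5 to week 12. They do not apply to a woman kept on 0.2 mg/hr at week 1.
- **That the arms will differ materially in blood pressure terminations.** The nearest controlled figure is transient lightheadedness of 6% against 4% in trials of intermittent therapy (I.1.1). An excess is plausible but unquantified. K.2.1 analyses by intention to treat, and J.2 seeks outcome data at an early termination visit.

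**Conclusion.** The point holds in a limited form. For a woman on 0.2 mg/hr who meets an I.1.2 limit at week 1, the visit and dosing sections contradict the safety section, with no stated precedence. The reduction option in I.1.2 and the reduction condition in J.1 criterion 2 cannot be applied at that dose, at week 1 or later. The text is wrong as written and concerns a safety rule, so it should be corrected even though few women are likely to be affected.

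The documents give no rate at which randomized women would meet these limits, so no count or effect on the primary analysis can be computed. The conclusion rests on reading the sections as written and on F.1.4 being the full list of treatment-phase doses.

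**What to change.** Reconcile F.1.6, H.2.5 A and B, I.1.2 and J.1 so that every blood pressure finding at every current dose (0.2, 0.4 and 0.6 mg/hr) leads to one stated action. A single table by dose and finding, referred to from all four sections, would do this. In particular:

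- make the sentences permitting women to remain on their dose in H.2.5 and F.1.6 agree with I.1.2 for women who meet one of its limits, by changing either side;
- state what applies at 0.2 mg/hr, where a reduction is not available, in both I.1.2 and J.1 criterion 2;
- word the low limit identically throughout, including whether one reading or both must be below it.

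The sponsor and the DSMB choose the action in each case; this review does not propose one. The cost is a protocol wording amendment and one table, with IRB review as M.1 requires. Design, sample size and analysis are unchanged.
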